**4. OBJECTIVES AND ENDPOINTS**

**Table 4.-1: Objectives and Endpoints**

Objectives	Endpoints

Primary
 
To establish the tolerability of the combination of nivolumab and daratumumab in participants with advanced or metastatic solid tumors.
	
Incidence of adverse events (AE), serious adverse events (SAE) and specific laboratory abnormalities (worst grade).

Secondary
 
 
• To evaluate the objective response rate (ORR) of nivolumab combined with daratumumab in participants with advanced or metastatic tumors in each cohort.
 
• To assess progression free survival (PFS) of nivolumab combined with daratumumab in participants with advanced or metastatic tumors in each cohort.
 
• To characterize the pharmacokinetics of nivolumab and daratumumab in participants with advanced or metastatic tumors.
 
• To characterize the immunogenicity of nivolumab and daratumumab in participants with advanced or metastatic tumors
 
	
 
• ORR, duration of response (DOR), best overall response (BOR) in each cohort, based on RECIST 1.1 criteria (Appendix 7).
 
• Median PFS in each cohort
 
• Pharmacokinetic parameters, influence of intrinsic and extrinsic covariates and potential exposure-response relationship will be characterized using integrated analyses.
 
• Immunogenicity of nivolumab and daratumumab will be assessed by ADA positivity
 

[REDACTED]
 
[REDACTED]
 
[REDACTED]
	
[REDACTED]

## **5. STUDY DESIGN**

### **5.1 Overall Design**

Study CA2099GW is an open-label, multi-center, Phase 1/2 study investigating the safety and efficacy of nivolumab in combination with daratumumab in participants with advanced or metastatic tumor types including TNBC, NSCLC, and PAC. As of 13-June-2018, only TNBC and PAC participants who are deriving clinical benefit will continue to be treated with the nivolumab plus daratumumab combination therapy; NSCLC participants will be treated with nivolumab monotherapy, only.

Enrollment of all tumor types is closed, as of 26-May-2018. The enrollment of participants with NSCLC is closed due to the lack of an efficacy signal. This decision was not related to any serious adverse events associated with the use of nivolumab in combination with daratumumab. The enrollment of participants with TNBC and PAC was previously closed as the study had met enrollment goals in these 2 cohorts.

Participants will be treated for a maximum of 24 months on study, or until confirmed progression, unacceptable toxicity, withdrawal of consent, or the study is discontinued by the sponsor. Study treatment can continue beyond initial investigator assessed progression as specified in [Section 7.1.5](#)

[figure not shown]
The study will consist of Screening, Treatment, and Follow-up. All safety data will be monitored on an ongoing basis throughout the study.

The duration of the study is anticipated to be approximately 3 years.

Please refer to [Section 7.8](#) for study termination criteria.

The study design schematic is presented in [Figure 5.1-1](#).

**Figure 5.1-1: Study Design Schematic**

Abbreviations: NSCLC= non-small cell lung cancer; PAC= pancreatic adenocarcinoma; NCB= triple-negative breast cancer; CR = complete response; PR = partial response; SD= stable disease; PD= progressive disease; Pre-tx = pretreatment; Q1W = every week; Q2W = every 2 weeks; Q4W = every 4 weeks; Q6W = every 6 weeks; Q12W = every 12 weeks

**Screening Period** (up to 28 days):

Participants will sign the informed consent form prior to undergoing any study-related procedures. Screening evaluations to determine eligibility will be performed within 28 days prior to the start of therapy (as outlined in Table 2.-1).

A baseline tumor imaging assessment will be performed prior to the start of therapy. Tumor tissue and peripheral blood must be provided for biomarker analysis. Sufficient, recent tumor tissue (fresh tumor biopsy or tumor tissue collected after the completion of the most recent prior therapy) obtained from a metastatic tumor lesion or from an unresectable primary tumor lesion which has

not been previously irradiated (formalin-fixed paraffin-embedded block (FFPE) or minimum of 25 slides, obtained from core biopsy, punch biopsy, excisional biopsy or surgical specimen) will be submitted to the central laboratory. If not enough tumor sample is available, the investigator has to contact the BMS study team to inform the BMS team if less than 25 charged unstained slides are available for the potential impact on biomarker testing.

#### Treatment Period:

During the Treatment period, (Table 2.-2) participants will receive (1) nivolumab 240 mg every 2 weeks from Week 3 to 24, then nivolumab 480 mg every 4 weeks from Week 25 and beyond, and (2) daratumumab 16 mg/kg every week for 8 weeks, then every 2 weeks for 16 weeks, and then every 4 weeks from week 25 onward, for a total treatment duration of 24 months. Due to the daratumumab infusion related reactions profile, the first 2 doses of daratumumab will be administered alone and nivolumab administration will start with the third dose of daratumumab. As of 13-June-2018, only TNBC and PAC participants who are deriving clinical benefit will continue to be treated with the nivolumab plus daratumumab combination therapy; NSCLC participants will be treated with nivolumab monotherapy. The treatment period will continue for a maximum of 24 months or until disease progression, occurrence of unacceptable toxicity, consent withdrawal, or the study is stopped by the Sponsor.

On-treatment tumor imaging assessments will occur every 6 weeks (+/-1 week) for the first 24 weeks, then every 12 weeks (+/- 1 week) until disease progression including participants who discontinue treatment due to unacceptable toxicity or until initiation of subsequent therapy, whichever occurs first. Treatment beyond initial investigator-assessed progression is permitted if the participant has an investigator-assessed clinical benefit and is tolerating study drug (Section 7.1.5). The investigator-assessed tumor response based on RECIST 1.1 criteria will be used for efficacy analyses. All participants will continue to be followed for safety after discontinuation of study medication during the Follow-up period. Participants who discontinue study drug due to toxicity will continue to have tumor assessments until disease progression or withdrawal of consent during Follow-up as specified in Table 2.-3.

Participants will be closely monitored for AEs and SAEs throughout the study. Participants who experience AEs that require discontinuation of one of the study drugs may be allowed to continue therapy with the other study drug, if deemed as in their best interest by both the PI and the BMS medical monitor. Participants must be deriving clinical benefit.

Participants may withdraw or discontinue at any time based on criteria in Section 8.1.

#### Follow-up Period:

All study participants who discontinue treatment will enter the Follow-up period, with visits scheduled on Days 30 and 100 from the last study drug dose, to monitor for AEs. Participants who discontinue study treatment due to toxicity will continue to be evaluated for efficacy until progression or initiation of subsequent therapy, whichever occurs first, as specified in Table 2.-3.

### **5.1.1 Data Monitoring Committee and Other External Committees**

Not applicable [REDACTED]

## 5.2 Number of Participants

Enrollment of all tumor types is closed, as of 26-May-2018. The enrollment of participants with NSCLC was closed due to the lack of an efficacy signal. This decision was not related to any serious adverse events associated with the use of nivolumab in combination with daratumumab. The enrollment of participants with TNBC and PAC was previously closed as the study had met enrollment goals in these 2 cohorts.

188 participants were enrolled in the study to ensure a total of 40 participants treated in each cohort, which assumed a screen failure rate of 25%. See [Section 10.1](#) for sample size determination.

Participants at least 18 years old, who have histologic or cytological confirmation of the following solid tumors were enrolled:

- Triple negative Breast Cancer, TNBC (Cohort A)
- Non-small cell lung cancer, NSCLC (Cohort B)
- Pancreatic adenocarcinoma Cancer, PAC (Cohort C)

## 5.3 End of Study Definition

[figure not shown]
The start of the trial is defined as first visit for first participant screened. End of trial is defined as the last visit or scheduled procedure shown in the Schedule of Activities for the last participant.

[REDACTED]

### **5.6 Duration of Treatment: 24 months**

The optimal duration of immunotherapy is currently unknown. However, because immunotherapy engages the immune system to control the tumor, continuous treatment as is required with targeted agents or cytotoxic therapy may not be necessary. Accumulating evidence from different clinical trials in different tumors types with nivolumab indicates that most of the responses are generally occurring early, with a median time to response of 2-4 months including in patients with NSCLC. and a recent analysis in a melanoma study suggests the majority of patients who discontinue nivolumab for toxicity maintain disease control in the absence of further treatment. For these reasons, in study CA2099GW, treatment will be given for up to 24 months in the absence of disease progression or unacceptable toxicity.

## **6. STUDY POPULATION**

For entry into the study, the following criteria **MUST** be met.

### **6.1 Inclusion Criteria**

#### **1) Signed Written Informed Consent**

- a) Participants must have signed and dated an IRB/IEC approved written informed consent form in accordance with regulatory and institutional guidelines. This must be obtained before the performance of any protocol related procedures that are not part of normal participant care.
- b) Participants must be willing and able to comply with scheduled visits, treatment schedule, laboratory **tests**, potential tumor biopsies, and other requirements of the study.

#### **2) Type of Participant and Target Disease Characteristics**

- a) Women with histologically or cytologically confirmed breast carcinoma who must meet all of the following:
  - i. Tumor must be “triple receptor negative” defined as ER/PR negative and HER-2 negative defined per 2013 American Society of Clinical Oncologists and College of American Pathologists (ASCO-CAP) guidelines.

AND

- ii. Participants must have had received 1 to 4 prior regimens for the treatment of metastatic (Stage IV) or locally advanced disease. There must have been progression on or following the last regimen or unacceptable adverse events requiring discontinuation or therapy.
- b) Participants with histologically or cytologically confirmed pancreatic adenocarcinoma who must meet the following:
  - i. Participants must not have clinically relevant ascites at baseline, such as ascites in need of paracentesis.  
AND
  - ii. Participants must have received only 1 prior chemotherapy regimen for the treatment of metastatic (Stage IV) or locally advanced disease. There must have been progression on or following the last regimen or unacceptable adverse events requiring discontinuation or therapy.
- c) Participants must have histologic or cytologic confirmation of NSCLC (per the seventh International Association for the Study of Lung Cancer [IASLC]) with squamous or nonsquamous histology that is advanced (metastatic and/or unresectable)
  - i. Participants must have no more than 2 prior lines of therapy including one line of platinum doublet chemotherapy.
  - ii. Participants who will receive study therapy as second line of treatment must have experienced disease recurrence or progression during or after one prior platinum doublet-based chemotherapy regimen for advanced or metastatic disease.
    - a. First line therapy is defined as therapy used to treat advanced disease. Each subsequent line of therapy is preceded by disease progression. A switch of an agent within a regimen in order to manage toxicity does not define the start of a new line of therapy.
    - b. Experimental therapies when given as separate regimen are considered as separate line of therapy and must have resulted in disease progression.
    - c. Maintenance therapy following platinum doublet-based chemotherapy is not considered as a separate regimen of therapy and could comprise continuation of one or more of the agents used in the first-line therapy regimen or switch to another non cross-resistant agent. The initiation of maintenance therapy requires the lack of progressive disease with frontline therapy.
    - d. Treatment given for locally advanced disease is not considered as a line of therapy for advanced disease. Participants with recurrent disease > 6 months after platinum containing adjuvant, neoadjuvant or definitive chemoradiation therapy given for locally advanced disease, who also subsequently progressed during or after a platinum doublet-based regimen given to treat the recurrence, are eligible. Adjuvant or neoadjuvant platinum-doublet chemotherapy (after surgery and/or radiation therapy) followed by recurrent or metastatic disease within 6 months of completing therapy is considered as first line therapy for advanced disease.

- iii. Participants who will receive study therapy as third line of treatment must have experienced disease recurrence or progression during or after a separate EGFR or ALK tyrosine kinase inhibitor (TKI) regimen in addition to one prior platinum doublet-based chemotherapy regimen (regardless of order of administration).
  - a. Participants who received an EGFR TKI (erlotinib, gefitinib or experimental) in addition to a platinum-based chemotherapy must have a tumor with a known activating EGFR mutation.
  - b. Participants with a tumor with EGFR wild-type or unknown EGFR mutation status who received an EGFR TKI after failure of a prior platinum-based chemotherapy are excluded.
  - c. Participants who received an ALK inhibitor (crizotinib or experimental) in addition to a platinum-based chemotherapy must have a tumor with a known ALK translocation.
- d) Participants must have measurable disease by CT or MRI per RECIST 1.1 criteria (radiographic tumor assessment must be performed within 28 days prior to first dose).
- e) Eastern Cooperative Oncology Group (ECOG) performance status of 0 or 1.
- f) Life expectancy of at least 3 months
- g) Must consent to tumor biopsy.
- h) Either a formalin-fixed, paraffin-embedded (FFPE) tissue block or unstained tumor tissue sections, obtained within 3 months prior to first dose, with an associated pathology report, must be submitted to the core laboratory for inclusion. Central lab must provide Interactive Response Technology (IRT) with confirmation of receipt of evaluable tumor tissue prior to study treatment. Biopsy should be excisional, incisional or core needle. Fine needle aspiration is unacceptable for submission. If not enough tumor sample is available, the investigator has to contact the BMS study team to inform the BMS team if less than 25 charged unstained slides are available for the potential impact on biomarker testing.
- i) Prior focal palliative radiotherapy to an isolated bone or soft tissue metastasis must be completed at least 2 weeks before study drug administration.
- j) All baseline laboratory requirements will be assessed and should be obtained within 14 days of first dose. Screening laboratory values must meet the following criteria:
  - i. WBCs  $\geq 2000/\mu\text{L}$  (growth factors not permitted within 1 week of study drug administration; pegylated growth factors not permitted within 3 weeks of first study drug administration)
  - ii. Neutrophils  $\geq 1500/\mu\text{L}$  (growth factors not permitted within 1 week of study drug administration; pegylated growth factors not permitted within 3 weeks of first study drug administration)
  - iii. Platelets  $\geq 100 \times 10^3/\mu\text{L}$  (transfusions not permitted within 72 hours prior to qualifying laboratory value)
  - iv. Hemoglobin  $\geq 9.0 \text{ g/dL}$  (transfusions not permitted within 72 hours prior to qualifying laboratory value; recombinant human erythropoietin not permitted within 3 weeks of study drug administration)
  - v. Estimated creatinine clearance by Cockcroft-Gault formula  $\geq 30 \text{ mL/min}$
  - vi. AST and ALT levels  $\leq 3 \times \text{ULN}$  or  $\leq 5 \times \text{ULN}$  if liver metastases are present

- vii. Total Bilirubin  $\leq 1.5 \times$  ULN (except participants with Gilbert Syndrome who can have total bilirubin  $< 3.0$  mg/dL)
- viii. Albumin  $\geq 3$  g/dL
- ix. For participants with pancreatic adenocarcinoma
  - a. Lipase  $\leq 1.5 \times$  ULN. Participants with lipase  $> 1.5 \times$  ULN may enroll if there are neither clinical nor radiographic signs of a pancreatitis
  - b. Amylase  $\leq 1.5 \times$  ULN. Participants with amylase  $> 1.5 \times$  ULN may enroll if there are neither clinical nor radiographic signs of a pancreatitis

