## 2) Prior/Concomitant Therapy

- a) Prior therapy with any T cell co-stimulation or checkpoint pathways, such as anti-PD-1, anti-PD-L1, anti-PD-L2, anti-CD137, or anti-CTLA-4 antibody, including ipilimumab and nivolumab; or other medicines specifically targeting T cells.
- b) Prior therapy with anti-CD38 monoclonal antibodies.
- c) Prior organ allograft.

- d) Treatment with any chemotherapy, radiation therapy, (except for palliative radiation therapy as indicated in inclusion criterion 2.i above), biologics for cancer, or investigational therapy within 28 days of first administration of study treatment (participants with prior cytotoxic or investigational products < 4 weeks prior to treatment might be eligible after discussion between investigator and sponsor, if toxicities from the prior treatment have been resolved to Grade 1 (NCI CTCAE version 4).

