### **1.3.3 Lesions with prior local treatment**

Tumor lesions situated in a previously irradiated area, or in an area subjected to other loco-regional therapy, are usually not considered measurable unless there has been demonstrated progression in the lesion.

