## **1.4 Specifications by methods of measurements**

### **1.4.1 Measurement of lesions**

All measurements should be recorded in metric notation (mm). All baseline evaluations should be performed as close as possible to the treatment start and never more than 30 days before the beginning of the treatment.

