4.1.1 Objective Response Rate

Objective Response Rate (ORR) is defined as the number of treated subjects who achieve a best response of complete response (CR) or partial response (PR) based on investigator assessments (using RECIST v1.1 criteria) divided by the number of all treated subjects. Best Overall Response (BOR) is defined as the best response, as determined by Investigator, recorded between the date of first dose and the date of objectively documented progression per RECIST v1.1 criteria or the date of subsequent therapy, whichever occurs first. For subjects without documented progression or subsequent therapy, all available response designations will contribute to the BOR determination. Subsequent therapy includes any therapy (systemic cancer therapy, surgery, radiotherapy).

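### The baseline scan can predate the end of permitted palliative radiotherapy, so shrinkage from that treatment can be counted as a response in the single-arm ORR

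*Protocol*

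**What the plan says.** **Scan date.** Protocol Section 6.1, 2) d) requires measurable disease and adds "radiographic tumor assessment must be performed within 28 days prior to first dose". Tables 2.-1 and 9.1.1-2 give the same 28 days. Appendix 7, 1.4.1 asks for baseline evaluations near the start of treatment, but its limit is "never more than 30 days before the beginning of the treatment".

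**Palliative radiotherapy.** Section 6.1, 2) i): "Prior focal palliative radiotherapy to an isolated bone or soft tissue metastasis must be completed at least 2 weeks before study drug administration". Section 6.2, 2) d) exempts this radiotherapy from the general washout.

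**Other prior treatment.** The same exclusion rules out chemotherapy, other radiation, "biologics for cancer, or investigational therapy within 28 days of first administration of study treatment". It then makes an exception: "participants with prior cytotoxic or investigational products < 4 weeks prior to treatment might be eligible after discussion between investigator and sponsor". The condition attached is resolution of toxicity, not a new scan.

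**Lesion choice.** Appendix 7, 1.3.3 says that lesions in an area already treated locally "are usually not considered measurable unless there has been demonstrated progression in the lesion".

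**Response.** Appendix 7, 3.1 measures a partial response as a 30% fall from the baseline sum of diameters. SAP 4.1.1 takes the best response "recorded between the date of first dose and the date of objectively documented progression", or up to subsequent therapy if that comes first.

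**Contrast.** Table 2.-1 and the screening text of Section 5.1 accept existing tumor tissue only if it was collected after the most recent prior therapy. The scan has no such rule.

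**The concern.** With no control arm, every fall from the baseline sum is credited to nivolumab plus daratumumab. If the scan is taken first and a target lesion is irradiated afterwards, the reference sum is the untreated size. The first on-study scan then shows the radiotherapy effect as well as any drug effect.

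The SAP recognises that other treatment confounds response: it closes the response window at any subsequent systemic therapy, surgery or radiotherapy. That rule acts only after first dose, and nothing comparable covers the interval between scan and first dose. Appendix 7, 1.3.3 speaks of areas already irradiated and says only that such lesions are usually excluded. It does not clearly reach a lesion selected on the scan and irradiated later.

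What is at stake is ORR by cohort, a secondary endpoint that the plan reads against 10% for TNBC and PAC. At 40 participants, few responders separate one reading from the other.

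**Working it through.** **1. Dates.** Inputs: scan no earlier than Day -28 (Section 6.1, 2) d)); radiotherapy ended by Day -14 (2) i)).
- Largest overlap for radiotherapy: 28 - 14 = 14 days. With the Appendix 7 window: 30 - 14 = 16 days.
- Chemotherapy and other treatment under the general rule: excluded within 28 days, and the scan lies inside those 28 days, so there is no overlap. The 30-day window would open at most 30 - 28 = 2 days. Otherwise overlap needs the exception for cytotoxic or investigational products.

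**2. What one irradiated lesion must do.** Let *w* be its share of the baseline sum, with all other lesions unchanged. A partial response needs shrinkage of 0.30/*w*:

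| Share of baseline sum | Shrinkage needed |
|---|---|
| 100% | 30% |
| 75% | 40% |
| 50% | 60% |
| 30% | 100% |
| below 30% | impossible alone |

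A share of 100% is possible, because one measurable lesion is enough for entry. Below 30% the lesion can still add to shrinkage elsewhere. Systemic treatment under the exception can act on all lesions, so this limit does not apply to it.

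**3. The plan's own figures** (Protocol 10.1, SAP 5). Power by normal approximation is Φ{[(p1 - p0)√n - 1.96√(p0(1 - p0))]/√(p1(1 - p1))}. With p0 = 0.10, p1 = 0.25 and n = 40 it is Φ{(0.9487 - 0.5880)/0.4330} = Φ(0.833) = 79.8%, as stated. The Clopper-Pearson interval for 8/40 is 9.05-35.65%, matching the tabulated 9.1-35.6%. At 9/40 it is 10.84-38.45%, which confirms 9 as the first count whose lower bound excludes 10%.

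**4. One false responder.** 1/40 = 2.5 points. It moves 8/40 (9.1-35.6%) to 9/40 (10.8-38.5%), across the 10% bound.

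**5. Range.** The documents do not say how many participants had such an overlap. Assume that carry-over adds 0, 2.5 or 5 points to a true ORR of 10%. The exact binomial chance of at least 9 of 40 is then:

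| Added points (assumed) | Response probability | P(at least 9/40) |
|---|---|---|
| 0 | 10.0% | 1.5% |
| 2.5 | 12.5% | 5.5% |
| 5 | 15.0% | 13.5% |

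**6. DOR and PFS.** Progression is a 20% rise, and at least 5 mm, from the smallest sum on study. Take an irradiated lesion of 40 mm and other lesions totalling 60 mm. If the irradiated lesion disappears, the smallest sum is 60 mm and growth of 0.20 × 60 = 12 mm elsewhere is progression. If it had stayed at 40 mm, the sum would be 100 mm and 20 mm would be needed. Radiotherapy shrinkage can therefore bring progression forward. It can also delay it, by offsetting growth elsewhere before the smallest sum is reached. The direction is not fixed.

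**The case against.** The strongest case is that the route is narrow and the decisions are past.

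- **Safeguards exist.** The radiotherapy is focal and to an isolated metastasis. Bone lesions are measurable only through a soft-tissue component. Up to five target lesions must represent all involved organs. New lesions or clear non-target growth mean progression. Responses need confirmation after at least 4 weeks. The document history describes the radiotherapy allowance as being for a non-index lesion, which suggests the intent. These points limit the frequency and stand. They do not close the gap: confirmation guards against measurement error, which lasting radiotherapy shrinkage would pass, and the current criterion does not carry the non-index restriction.
- **Redaction.** Much of Section 7.7, including the imaging precautions that Table 9.1.1-1 refers to, is not visible. The claim can only be that no visible passage orders the dates.
- **Timing.** Enrollment is closed, the TNBC and PAC interims are done, and the NSCLC combination was stopped before 20 were treated. The SAP now covers a synoptic close-out report without p-values. This stands: rewriting eligibility would change nothing, and the 20% bound at n = 40 no longer applies to NSCLC.

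A reader might infer more than the documents support:

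- **That chemotherapy carries the same risk.** Under the 28-day window it does so only through the sponsor exception.
- **That the error runs only upward and lengthens DOR and PFS.** Step 6 shows otherwise for DOR and PFS. For ORR, carry-over pushes upward, but an older scan also counts growth before first dose against the drugs.
- **That entry without progression is the same problem.** TNBC and PAC participants may qualify after stopping for toxicity: "There must have been progression on or following the last regimen or unacceptable adverse events requiring discontinuation or therapy". Such a participant may still benefit from the last regimen, but that can happen whatever the scan date, and a check based on dates would not detect it.
- **That the futility decisions were distorted.** With the assumed 2.5 or 5 points, the chance of 2 or fewer of 20 at a true 10% falls from 67.7% to 53.5% or 40.5%. Those analyses are finished and rested on the totality of evidence. Upward bias also cannot explain the sponsor's conclusion that efficacy did not warrant continuing the combination.

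**Conclusion.** The concern holds as a limited gap in the visible text. A compliant baseline scan can precede the end of permitted palliative radiotherapy by up to 14 days (16 with the Appendix 7 window). No visible rule orders the two dates or removes a lesion irradiated after the scan from the target sum. Prior-treatment shrinkage can therefore be counted as response; the documents do not show that it was.

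The size is unknown. The shift from 8/40 to 9/40 and the tail probabilities of 5.5% and 13.5% are illustrations. They rest on assumed carry-over of 2.5 or 5 points, a true ORR of 10%, and the planned 40 per cohort, since the treated numbers per cohort are not stated. They show that one or two affected participants could matter to how a TNBC or PAC result reads against 10%. For DOR and PFS no direction can be claimed. This is a cheap improvement to the close-out report, not a flaw that invalidates the ORR.

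**What to change.** Add to SAP 4.1.1 and 7.4.1, in words such as:

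> The number and percentage of treated subjects whose baseline tumor assessment is dated before the end of their last prior anticancer therapy (systemic or radiotherapy) will be presented by tumor type. ORR with its exact Clopper-Pearson 95% CI will also be presented counting these subjects as non-responders. This supportive analysis is read alongside the main ORR and does not replace it.

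State how partial end dates of prior therapy are handled and how many were imputed.

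The cost is one count and one ORR row per cohort, assuming that the database holds scan dates and prior-therapy end dates. If nobody is affected, the ORR is unchanged and the report can say so. The downside is that the supportive ORR may be slightly conservative: it discards genuine responses among flagged participants, including any whose irradiated lesion was not a target lesion.

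Separately, reconcile the 28-day baseline window in Section 6.1 with the 30-day limit in Appendix 7, 1.4.1, so that one definition of a valid baseline assessment governs the analysis.
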